Birth asphyxia causes up to 1.8 million newborn deaths and stillbirths every year. This global tragedy can be prevented by effectively Helping Babies Breathe at the time of birth. Helping Babies Breathe (HBB) (Appendix 1) is a newborn stabilization course that has been shown to reduce early neonatal mortality by up to 47% in Tanzania.(1) Significant reduction in intrapartum still births and first day mortality have also been demonstrated in other low and middle-income countries. (2, 3) The knowledge and skills acquired in this course, however, have been shown to rapidly deteriorate over time, with skills deteriorating more than knowledge. (4) The largest systematic review on this topic suggests that although not commonly included in resuscitation programs, refresher training is likely necessary to improve the impact on neonatal mortality.(5) Mduma et al have demonstrated that frequent brief on-site simulation with the HBB program can have a sustained impact on mortality.(6) Furthermore, regular, low intensity, manikin-based skills training with peers has been shown to allow workers to maintain bag mask ventilation skills at one year. (7) We propose to improve sustainability of HBB's impact by increasing skills retention with an innovative mobile application called HBB Prompt. If successful, our application provides a novel, low-cost method for providers to receive regular simulation training with peers.

HBB Prompt will be an interactive tool that guides frontline providers through the steps needed to save newborn babies at birth. HBB Prompt will facilitate individual and group training in health facilities using the Low Dose High Frequency model (LDHF) for resuscitation skills retention. Our group has successfully developed and tested a related application for the Neonatal Resuscitation Program (NRP), the newborn stabilization algorithm used in North America.(8) We will use lessons learned from our previous work to robustly develop HBB Prompt by integrating human factors and user-centered design approaches. We will engage end-users and HBB Master Trainers to iteratively collect feedback to develop HBB Prompt for both individual and small group resuscitation practice. Our iterative approach will mitigate the common scenario of mobile health (mHealth) solutions unable to achieve sustained success at scale due to lack of comprehensive input from frontline users. We will pilot the app at a single centre and compare it to a control site for HBB skills retention.

Hypothesis: Applying a user-centered design approach of collecting iterative qualitative data from end-users regarding learning needs and facilitators and barriers to HBB skills maintenance will enable creation of a mobile app that will improve skills retention in an intervention group versus a control group.

Objectives

1. To develop a refined HBB Prompt app through user-centered design involving input from frontline birth attendants in Uganda.
2. To train a minimum of twenty health workers from two district hospitals in Southwestern Ugandan in HBB 2.0 and Essential Care for Every Baby within 6 months of the start of the project.
3. To determine the impact of the HBB Prompt app on HBB skills retention of providers in the intervention site compared with providers in the control site (higher average OSCE B test scores) 12 months after training.

Objective 1: To develop a refined HBB Prompt app through user-centered design involving input from frontline birth attendants in Uganda.

Phase 1a

We will collect observational data on the process of HBB training and HBB skills in action to determine barriers and habits of formation that could be redirected or improved. This processes and skills habits may not be apparent to end-users. This will be conducted by review of audio-visual footage of HBB training sessions. Video recordings will be obtained using roof mounted video equipment from the Mbarara University Simulation center after full participant consent.

We will then solicit qualitative feedback regarding the perceived facilitators and barriers to learning and maintaining HBB knowledge and skills through individual interviews and separate focus groups organized by provider level of experience to allow for exploration of different needs for skills acquisition and skills maintenance. We aim to recruit 4-6 participants per group to reach saturation of themes.

Focus group composition will be:

- 1) HBB Master trainers and facilitators,
- 2) Target end users of the HBB program such as previously trained HBB providers and
- 3) Pre-service trainees (total of 3 groups).

The anticipated provider types within each group would include the following:

- Nurses and midwives
- Medical officers

- Consultant physicians (pediatricians)
- Medical and nursing students typically in their clinical rotations.

Interview and focus group questions will address:

- Personal experiences regarding successes and challenges in stabilization of the newborn
- Barriers encountered and perceived needs to enable optimal maintenance of skills
- Personal experiences regarding successes and challenges of the actual HBB training sessions. Discussion about which parts enhanced their learning (e.g. simulation, graphics, anecdotes from others, etc) and which parts made it difficult to learn skills
- How they would design a solution to aid them (participatory design) to overcome barriers and/or to enhance their ability to use and maintain HBB knowledge and skills
- Whether they have participated in any refresher courses and what they thought of the utility of refresher training

Phase 1b: Development of HBB Prompt app through user-centred design

1. With the assistance of the project team's knowledge and previous experience with neonatal resuscitation and HBB, a team of engineers from Mbarara University of Science and Technology (MUST) will work together with the investigator team to create a prototype app, HBB Prompt v0. The app will be designed on the Android platform. The Android platform was chosen for a number of reasons including a high usage of Android devices in Uganda, being open source and accessible on inexpensive devices, which will make the app more amenable for scale-up.
2. With input from the team's specialist in human factors and user-centred design, data gathered from Phase 1a will be integrated into HBB Prompt v0 to create HBB Prompt v1.
3. Phase 1b.1 to Phase 1b.3 will be an iterative process of feedback and adaptation of the app where usability and feasibility testing of the prototype app will be conducted to determine the optimal and desired features prior to pilot testing in Phase 2a.
 - a. Providers from the same groups in Phase 1a will participate in three sessions (Phases 1b.1 – 1b.3) where they will have time to explore the app and then use the app in simulated neonatal resuscitation training, after which they will provide feedback in focus group discussions and in short interviews. This process will allow the users to better understand how the app may work in real time to provide targeted suggestions to further improve the app. Both focus group discussions and interviews will be voice recorded transcribed and analyzed to inform further app development.
 - b. Focus group discussion questions will address:
 - i. content, interface, navigation, functionality, customizability, usability
 - ii. where participants see the use of the app taking place

- iii. how can the app be further modified or improved to achieve their desired functionality or fill the gaps that are identified with HBB learning
- c. The goal is to have:
 - i. 5 participants per group type (3 groups) = $5 \times 3 = 15$
 - ii. Interviews (15-30min/) for experience level (3 x 3)

Objective 2: To train a minimum of twenty health workers from two district hospitals in Southwestern Ugandan in HBB 2.0 and Essential Care for Every Baby (ECEB) within 6 months of the start of the project.

Phase 2a

We will train a minimum of 20 frontline health providers (10 per hospital) from two district hospitals in southwestern Ugandan in HBB 2.0 and ECEB. HBB and ECEB training will be conducted by national trainers in the ratio of 1 trainer to 6 providers. Providers will undergo ECEB training in addition to HBB as these training programs are recommended by the Uganda Ministry of Health to be offered together.

HBB 2.0 training takes place over one day and ECEB training over two days. Participants will be invited from both hospitals to any one episode of training to minimize the number of frontline birth attendants in trainings at any single time.

One hospital will be randomly selected and its providers will have access to the most updated version of HBB Prompt (beta) at the end of the trainings (Intervention arm). The control group will not have exposure to the HBB Prompt app post training.

Participants in both centers will be asked to achieve a minimum practice target of once per day. Our recommended frequency to use the app will be once per shift (i.e. run through 1 simulation per person as a pair). An HBB article from earlier this year showed the greatest improvement when health workers practiced at the beginning of every shift. As it may be difficult to ensure that it is done at the beginning of shift, we will leave the timing of once a shift practice at the discretion of providers. Whenever a new team comes on, they will be recommended to ask the previous team if they did a simulation practice. If not, then they will remind the outgoing team to complete it. These recommendations on frequency of practice will be offered at both the intervention and control sites. All sites will receive resuscitation practice mannequins and a resuscitation practice table.

We will present to the Health Facility team the results of their HBB simulation practice frequency as captured by the HBB Prompt app analytics in the intervention arm. This app analytics data on frequency of practice will be presented to the health facility every two months during the one year study period. The app will be designed to generate both individual and group (facility) practice frequency. Both intervention and control arms will have a standard log-book to record frequency of practice. The accuracy of the log-book will be compared to the data retrieved from app analytics in the intervention arm.

Objective 3: To determine the impact of the HBB Prompt app on HBB skills retention of providers in the intervention site compared with providers in the control site.

1. Primary outcome: comparison of OSCE B scores in intervention (HBB Prompt) vs. control group. (17 out of 23 constitutes a pass score)
 - a. At 0 months, (immediately before and after training)
 - b. At 3 months
 - c. At 6 months (midline)
 - d. And at 12 months (endline)
2. Measures during the 12-month period of intervention in HBB Prompt site and control site at two unannounced visits (4 months, 9 months):
 - i. HBB 2.0 Knowledge check (18 questions)
 - ii. Bag and mask ventilation skills check (score out of 14)
 - iii. OSCE A (score out of 12, 9 out of 12 constitutes pass score)
 - iv. In addition to the OSCE skills checklist as scored by raters, we will use the Augmented Infant Resuscitator (AIR) to objectively measure quality of newborn resuscitation during every ventilation epoch. AIR records time stamped data on ventilation quality, such as presence of air leak or obstruction and ventilation rate (www.air-device.com).
 - b. Data on potential confounders will be collected for each site (volume of deliveries, workload in labor and delivery, burnout, motivation, baseline supervision, experience, previous training, provider level, number of patients/areas each provider is responsible for, length of time provider has been in practice, availability of equipment, availability of an HBB algorithm posted at the bedside.)
 - c. Other clinical outcomes will be collected from the Ministry of Health Birth Register: For each patient: date of birth, time of birth, birth weight, death before discharge, admission to nursery, 1 and 5 minute Apgar scores, resuscitation status at birth and resuscitation outcome.
 - d. Reports generated and presented to each site every 2 months: frequency of practice, number of deliveries, number of infants requiring bagging, fresh stillbirths, neonatal mortality in hospital
3. App analytics
 - a. Pattern of usage
 - i. Which components of the app are being used?
 - training mode, simulation mode, help videos, quizzes
 - b. Frequency (login, page use), purpose device ID
 - i. Is low dose high frequency happening? – Frequent, short duration access?
 - c. Self practice vs. peer or group practice
 - d. Trends for scores for simulations and quizzes

4. We will conduct exit focus group discussions and interviews at both intervention and control sites:
 - a. For Intervention site providers:
 - i. Facilitators and barriers to implementing and maintaining HBB skills
 - ii. Did HBB Prompt help?
 - iii. Did HBB Prompt meet end-user needs
 - iv. Any suggestions for further improvement
 - v. Feasibility and sustainability of scale-up
 - vi. HBB Prompt specifics: content, interface, navigation, functionality, customizability, usability
 - b. For Control site providers:
 - i. Facilitators and barriers to implementing and maintaining HBB skills
 - ii. Discussion about ideas to facilitate skills maintenance
 - c. For both sites:
 - i. Perception of workload in labor and delivery, burnout, motivation
 - ii. Interviews only: description of baseline supervision, number of patients and areas each provider is responsible for, availability of equipment for practice and for clinical care (e.g. bag-mask ventilator, HBB algorithm)

Randomization

A random sequence generator will be used to determine a random number just prior to the start of phase 2. If the random number is odd, then Itojo will be the intervention site. If the number is even, then Kitagata will be the intervention site.

Study setting

Southwestern Ugandan (Itojo Hospital, Ntungamo District; Kitagata Hospital, Sheema District). Each study site will have HBB practice corners established and equipped with both resuscitation mannequins and resuscitation bag and mask devices.

Study duration

18 months in total, 4 months for phase 1 and 12 months for phase 2 and 2 months for data analysis.

Participant eligibility criteria and enrolment

Study Population Eligibility: We will conduct the study in an area where HBB is recommended as the training program for newborn resuscitation

Inclusion Criteria: Frontline birth attendants involved in the delivery or care of babies in the maternity ward, theater or pediatric wards with a possibility of involvement in newborn resuscitation.

Exclusion Criteria: Health workers providing care in other wards other than maternity and pediatrics.

Enrolment: Using community entry processes, the medical superintendents of each hospital will be approached and requested to allow the study to be conducted in the Hospital. Once consent is obtained from the superintendent, individual frontline birth attendants will be approached and consented to be part of the study before training sessions are conducted.

Data Analysis

Phase 1

Audio recordings from focus groups and interviews will be transcribed. Transcripts will be reviewed for themes using a grounded theory approach. Data analyses will take place after each iteration of phase 1b to incorporate feedback to improve and adapt each version of the HBB Prompt prototype. At least two investigators will independently read all transcripts at least twice to obtain an overall understanding, identify data codes and ensure that all comments are carefully considered and included. Categories within the themes will then be identified, and any relationships among themes determined. As data are entered into the analyses, categories will continue to be generated, until there is no new data that cannot be categorized under existing codes. When this occurs, it is likely that a range of functions and features of an ideal mobile app as a learning tool for HBB will have been categorized. Further, we will also likely have categorized an assortment of barriers and facilitators to skills maintenance and implementation of HBB Prompt. A similar analytic approach has previously been successfully used in the development of an osteoporosis clinical decision support tool (10).

Phase 2

Comparison of intervention versus control for the following outcomes will be analyzed at each time point using the Mann-Whitney U test:

- Primary outcome: OSCE B score at 12 months
- Secondary outcomes:
 - OSCE B scores at 0, 3, and 6 months
 - At two unannounced site visits (months 4 and 9)
 - Knowledge check score
 - BMV skills check score
 - AIR data
 - Percentage of time with correct ventilation rate
 - Percentage of time with air leak during ventilation
 - Percentage of time with obstructed airway during ventilation
 - Time to effective ventilation
 - OSCE A score

Additionally, comparison of OSCE B score after training at 0 months and at 12 months within each arm using the Wilcoxon-signed rank test

	0 months	3 months	4 months	6 months	9 months	12 months
OSCE B	Pre/post HBB training	x		x		x
OSCE A			x		x	
Knowledge check			x		x	
Bag-mask skills			x		x	
AIR			x		x	

Descriptive statistics compared between intervention and control for:

- Demographic data and potential confounders (volume of deliveries, workload in labor and delivery, burnout, motivation, baseline supervision, experience, previous training, provider level, number of patients/areas each provider is responsible for, length of time provider has been in practice, availability of equipment, availability of an HBB algorithm posted at the bedside)
- Other clinical outcomes: death before discharge, admissions to the nursery, number of deliveries, number of infants requiring bagging, fresh stillbirths, neonatal mortality prior to discharge
- Frequency of practice, self vs. group practice, skills practiced

Qualitative data from focus groups and interviews:

- Similar to in phase 1, audio recordings will be transcribed and reviewed using a grounded theory approach. Coded themes and categories will be compared descriptively between participants in the intervention versus the control groups.

Budget Summary

Budget category	Total CAD
Remuneration - funding recipient's employees	35,441
Fees - Subcontractors	19,642
Reimbursable Travel Costs	9,960
Reimbursable Goods and Supplies	9,304
Reimbursable Equipment Costs	2,640
Reimbursable Project Administration Costs	2,845
Sub-grants	20,000
Total Project in CAD	99,831

References

1. Msemo G1, Massawe A, Mmbando D, Rusibamayila N, Manji K, Kidanto HL, Mwizamuholya D, Ringia P, Ersdal HL, Perlman J. Newborn mortality and fresh stillbirth rates in Tanzania after helping babies breathe training. *Pediatrics*. 2013 Feb;131(2):e353-60. doi: 10.1542/peds.2012-1795. Epub 2013 Jan 21.
2. Kc A1, Wrammert J2, Clark RB3, Ewald U2, Vitrakoti R4, Chaudhary P4, Pun A2, Raaijmakers H2, Målqvist M2. Reducing Perinatal Mortality in Nepal Using Helping Babies Breathe. *Pediatrics*. 2016 Jun;137(6). pii: e20150117. doi: 10.1542/peds.2015-0117.
3. Goudar SS1, Somannavar MS, Clark R, Lockyer JM, Revankar AP, Fidler HM, Sloan NL, Niermeyer S, Keenan WJ, Singhal N. Stillbirth and newborn mortality in India after helping babies breathe training. *Pediatrics*. 2013 Feb;131(2):e344-52. doi: 10.1542/peds.2012-2112. Epub 2013 Jan 21.

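### App analytics see only practice run in the app, so they cannot serve as the accuracy standard for a log-book of all practice; the between-arm description of practice frequency should rest on the log-book

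*Protocol*

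**What the plan says.** The relevant text is in three places in the Protocol.

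- **Objective 2, Phase 2a.** "Both intervention and control arms will have a standard log-book to record frequency of practice". Its check is made in one arm only: "The accuracy of the log-book will be compared to the data retrieved from app analytics in the intervention arm". Feedback to the intervention hospital comes from the same analytics: "We will present to the Health Facility team the results of their HBB simulation practice frequency as captured by the HBB Prompt app analytics", with the interval given as "This app analytics data on frequency of practice will be presented to the health facility every two months during the one year study period". On what is available for practice: "All sites will receive resuscitation practice mannequins and a resuscitation practice table". On the control arm: "The control group will not have exposure to the HBB Prompt app post training". The daily practice target applies to both centres and does not mention the app; a separate recommendation is to use the app once per shift, in pairs.
- **Objective 3.** Item 2d covers both hospitals and names no data source: "Reports generated and presented to each site every 2 months: frequency of practice". Item 3 lists the analytics: which app components are used, logins and page use with device ID, self versus peer or group practice, and trends in simulation and quiz scores.
- **Data Analysis, Phase 2.** Among the descriptive comparisons between arms is "Frequency of practice, self vs. group practice, skills practiced", again with no source named. The primary outcome is the OSCE B score at 12 months.

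**The concern.** An accuracy check needs a reference that covers at least what the checked instrument covers. Here the reference is narrower. The log-book is the same form in both arms, and the control arm has no app, so the form must be able to record practice without one. Analytics can hold only what happens inside the app. Any genuine manikin session at the intervention hospital without the app is a correct log-book entry with no counterpart in the analytics, and the comparison as worded would count it against the log-book.

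What is at stake is the credibility and interpretation of the practice-frequency results. The background to the protocol rests the app on a low-dose, high-frequency model of practice, so how often each hospital practised is the natural explanatory variable for any difference in skills retention. The log-book is the only practice measure both arms share. A check that can make it look inflated in one arm, and says nothing about its error in the other, weakens that measure. Because the analysis section names no source, it also leaves room for analytics in one arm to be set beside log-book counts in the other.

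**Working it through.** The protocol gives no figure on this point, so there is nothing to reproduce. The check is a reading of the sections against each other, followed by simple arithmetic.

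**1. Coverage of each measure**

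| Measure | Intervention | Control | What it can record |
|---|---|---|---|
| Log-book | yes | yes | practice with or without the app |
| App analytics | yes | no | sessions in the app only |

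The last cell is an inference from the items listed under Objective 3, item 3; the protocol does not state it.

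**2. Can app-free practice occur at the intervention hospital?** Yes. Phase 2a supplies mannequins and a practice table to all sites, the Study setting section adds practice corners with bag and mask devices at each hospital, and the daily target is not tied to the app. How common it would be is unknown.

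**3. Size of the artefact.** Let N be the true number of sessions and s the share done without the app. Analytics show N(1-s). An error-free log-book shows N. The apparent over-recording is

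N / [N(1-s)] - 1 = s/(1-s).

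| s (assumed) | Analytics show, of true practice | Apparent over-recording by a perfect log-book |
|---|---|---|
| 0% | 100% | 0% |
| 10% | 90% | 0.10/0.90 = 11% |
| 25% | 75% | 0.25/0.75 = 33% |
| 50% | 50% | 0.50/0.50 = 100% |

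The second column is also what the facility would be told of its own practice if the two-monthly report rests on analytics alone. There would be about 12/2 = 6 such reports.

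**4. The artefact can also hide error.** If the log-book captures only a share c of sessions, the ratio of log-book to analytics is c/(1-s), which equals 1 whenever c = 1-s. With s = 25%, a log-book that misses 25% of sessions would appear exactly right. So the comparison of totals identifies neither over-recording nor under-recording unless s is known. Two further features could shift the ratio: in paired practice one login might stand for two people, and logins include use of videos and quizzes, which is not manikin practice. The breakdown by mode and by self or group practice in Objective 3, items 3a and 3c, may allow these two to be handled. It cannot reveal sessions that never touched the app.

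**5. Feedback.** Phase 2a names analytics as the source for the intervention hospital. Objective 3, item 2d promises practice-frequency reports to both hospitals. The control hospital has no analytics, so by inference its report must use the log-book. Interval and existence of feedback are equal by arm; the source is not.

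**The case against.** The best case for the protocol is that a common measure exists by design. The log-book is kept in both arms, analytics are an extra in one, and nothing says the two will be set against each other across arms. The source of a descriptive variable can be left to the analysis plan. The protocol says only that accuracy will be compared; it has no threshold and no step that discards the log-book. App use once per shift is recommended, so the app-free share may be small. The log-book form is not shown and may already mark app use. Feedback from analytics may be intended as part of the intervention.

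Much of this stands, and it limits the point. It does not rescue the check as worded: the reference is narrower than what it judges, and no later analysis plan can recover whether a session used the app if that was not recorded at the time.

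Stronger readings are tempting and are not supported:

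- *That practice is measured differently in the two arms.* The same log-book is kept in both.
- *That the intervention hospital alone receives feedback, or is shown individual counts.* Item 2d sends reports to both sites at the same interval. Phase 2a says the app can generate individual counts, but not that these are presented; the presentation is to the facility team.
- *That the protocol's question on whether low-dose, high-frequency practice is happening would be confounded between arms.* That question sits under app analytics and concerns access to the app in the intervention arm.
- *That a 12-month OSCE B difference would reflect audit and feedback and not the app.* A different feedback source could in principle act as a co-intervention, but the protocol gives no basis for its size or direction.

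**Conclusion.** The point holds in a limited form. The planned accuracy check uses a reference that cannot see app-free practice, so it would show a correct log-book as over-recording by s/(1-s). That is nothing if every intervention session uses the app, and 11% to 100% if 10% to 50% of sessions do not. The shares are assumptions; the protocol gives none. The conclusion also rests on two inferences: that analytics register only app sessions, and that the log-book does not already mark app use. The check in one arm tells the reader nothing about log-book error in the control arm.

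The effect is confined to the practice-frequency results and how they are interpreted. OSCE B scores are not derived from practice counts, and the primary comparison stands or falls without them. The change is still worth making before Phase 2 starts, because the missing item has to be recorded session by session.

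**What to change.** 1. **Log-book:** add a with-app/without-app mark to the standard form.
2. **Check against analytics:** restrict it to app-marked entries and describe it as agreement for app sessions, not accuracy of the log-book.
3. **Between-arm description:** state in Data Analysis, Phase 2 that frequency of practice is taken from the log-book in both arms. Report analytics separately, as app usage in the intervention arm.
4. **Two-monthly reports:** reconcile Phase 2a with Objective 3, item 2d, so that both hospitals receive log-book frequency in the same format. If analytics feedback is also given at the intervention hospital, declare it as part of the intervention. There is no need to drop it; showing both counts side by side keeps the automatically recorded information.

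The cost is one extra log-book column and a few sentences of text. The new mark is itself self-reported, so a mismarked entry would still disturb the agreement figure, and log-book error in the control arm would remain unmeasured.

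### Does listing OSCE B at months 0, 3, 6 and 12 under the primary outcome leave the trial without a single primary test?

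*Protocol*

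**What the plan says.** The protocol describes the OSCE B comparison in four places.

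- **Objectives, item 3** sets the aim as "higher average OSCE B test scores) 12 months after training". It does not use the word primary.
- **Objective 3, item 1** states "Primary outcome: comparison of OSCE B scores in intervention (HBB Prompt) vs. control group" and lists months 0, 3, 6 and 12. Month 0 is described as "At 0 months, (immediately before and after training". Month 6 is tagged as midline and month 12 as endline. None is called primary.
- **Data Analysis, Phase 2** states "Primary outcome: OSCE B score at 12 months" and, under the secondary outcomes, "OSCE B scores at 0, 3, and 6 months". The lead-in reads "Comparison of intervention versus control for the following outcomes will be analyzed at each time point using the Mann-Whitney U test". A separate Wilcoxon signed-rank analysis is a "comparison of OSCE B score after training at 0 months and at 12 months within each arm".
- **The schedule table in Data Analysis, Phase 2** shows OSCE B as "Pre/post HBB training" at month 0, then at months 3, 6 and 12.

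Objective 2, Phase 2a adds that the intervention hospital receives the app when the trainings end.

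**The concern.** There are two grounds for unease.

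First, months 0, 3 and 6 stand under the primary outcome in one section and under the secondary outcomes in another. A reader who took the primary outcome only from Objective 3 would find several candidate time points and no rule for choosing among them. If the most favourable could be reported as primary, the chance of a false-positive headline would exceed the nominal level.

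Second, month 0 appears as an outcome in both sections, and the analysis section tests it between arms. The pre-training score is taken before anyone has the app, and on the natural reading the post-training score is too. A difference at month 0 therefore tells us how alike the two hospitals were at the start. Presented as an outcome, it could be mistaken for an effect of the app.

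**Working it through.** **1. The texts side by side**

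| Place in the protocol | Time points | Status given |
|---|---|---|
| Objectives, item 3 | 12 | target of the objective |
| Objective 3, item 1 | 0 (pre, post), 3, 6, 12 | under the primary outcome, none singled out |
| Data Analysis, Phase 2 | 12 | primary |
| Data Analysis, Phase 2 | 0, 3, 6 | secondary |
| Schedule table | 0 (pre, post), 3, 6, 12 | when OSCE B is measured |

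The second and fifth rows hold the same time points. Item 2 of Objective 3 is built the same way, as measures with their visit times. Item 1 therefore reads most naturally as the primary measure and when it is taken. Only the analysis section assigns primary and secondary status to individual months, and Objectives, item 3 agrees with it.

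**2. What would be at stake under the other reading**

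The protocol gives no significance level, power or sample-size calculation, so there is no stated figure to reproduce. The inputs are 10 providers per arm (the planned minimum in Objective 2, Phase 2a), the Mann-Whitney test (Data Analysis, Phase 2) and an assumed two-sided 5% level per test.

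- One test, 10 against 10, no ties: the largest rejection region not exceeding 5% is min(U) ≤ 23. Its exact two-sided size is 0.0433; min(U) ≤ 24 gives 0.0524.
- Any of months 3, 6 or 12, if independent at exactly 5%: 1 − 0.95³ = 0.143. This is an upper guide, because repeated scores on the same providers are correlated.
- Any of months 3, 6 or 12, simulated with the exact test and no hospital effect: about 0.12, 0.11 and 0.10 at within-provider correlations of 0.3, 0.5 and 0.7.

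The move from about 4% to 10–12% arises only if the analysis section is set aside.

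**3. A limit on these figures**

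They assume that the hospitals do not differ. The Randomization section allocates one hospital to each arm, so any hospital difference goes straight into the comparison. Simulating the single 12-month test with a random hospital effect gives a rejection rate, with no app effect, of about 9% at an assumed intraclass correlation of 0.05 and about 15% at 0.10. The 4.3% shows only that naming one time point adds no multiplicity. It is not the error rate of this trial.

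**4. Month 0**

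The pre-training score precedes app access by definition. The post-training score is taken immediately after training, and access comes when the trainings end; the analysis section itself uses that score as the starting value for the within-arm comparison. The role of month 0 is thus visible in the text. Calling it baseline would keep both measurements, the Wilcoxon reference and the report by arm. Only a heading, and perhaps a p-value, would change.

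**The case for a change.** The case for a correction is fair. Item 1 is worded as an outcome, a comparison of intervention with control, and not as a timetable. The two sections do give months 0, 3 and 6 different status. The month-0 point holds whichever section governs: the same post-training score serves as a starting value in one analysis and as a between-arm outcome in another, and the secondary-outcome line does not say which of the two month-0 scores it means. The edit would cost almost nothing.

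All of that stands as a description of the text. It does not show that anyone following the plan would reach a different result. An analyst works from the analysis section, which is unambiguous about the primary time point. A month-0 comparison between two hospitals is useful to see, and the protocol nowhere calls it an effect of the app. The order of the post-training score and app release is not stated, but the natural reading puts the score first and no passage contradicts it. That is operational detail, not an error.

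**Conclusion.** The inconsistency is real but clerical, and no change to the plan follows. The protocol, read as a whole, fixes one primary comparison: OSCE B at 12 months by Mann-Whitney, with months 0, 3 and 6 secondary. Multiplicity inflation of the primary result under that reading is nil. The 10% to 12% figure depends on disregarding the analysis section and on the assumed level, correlations and absence of a hospital effect, so it should not be cited as a property of this trial.

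Treating the month-0 scores as baseline is what a sensible analyst would do when reporting. It alters neither the primary test nor the data collected. Should the protocol be revised for another reason, item 1 could be aligned with the analysis section in passing, but nothing depends on it.
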